3.2.2. Secondary Efficacy Endpoints

The secondary efficacy endpoints include several more representations of the cough counts from the VitaloJAK monitor, as well as scores from several patient-reported outcomes captured via questionnaire or electronic device.

For the cough counts, the secondary efficacy endpoints further explore the ratio of the reduction while awake and while asleep, as well as binary measures of whether patients achieved a 30%, 50%, and 70% reduction threshold. These are:

- A reduction from baseline in the number of coughs per hour in 24 hours by ≥30%, ≥ 50%, and ≥70%
- The ratio of the number of coughs per hour while awake after administration of study drug for 4 weeks to that at baseline.
- A reduction from baseline in the number of coughs per hour while awake by ≥30%, ≥ 50%, and ≥70%
- The ratio of the number of coughs per hour while asleep after administration of study drug for 4 weeks to that at baseline.

Further secondary endpoints draw from the results of several questionnaires or instruments reported during the study. The relevant endpoints are listed below:

- The change from baseline in weekly cough severity as assessed on the Visual Analog Scale (VAS) via the electronic tablet
- The change from baseline through Day 7 in daily cough severity as assessed on the VAS via the eDiary
- The change in Leicester Cough Questionnaire (LCQ) total score from baseline
- Whether or not the patient achieved an increase of ≥ 1.3 points (ie, improvement) in the LCQ total score from baseline
- The change in ICIQ-SF score from baseline
- The change in SF-36 (version 2) Physical Component Summary (PCS) and Mental Component Summary (MCS) scores from baseline, and the change from baseline in each of the 8 domain scores.
- The Patient Global Impression of Change (PGIC)

The VAS will be presented as a numerically labelled linear scale from 0-100 mm, where the patient is asked to indicate the severity of the cough. Higher VAS scores correspond to higher cough severity. The weekly cough severity will be captured at Visits 1, 2, 4, 5, and 6, and/or at the time of discontinuation of study drug, via an electronic tablet. The daily cough severity will be captured via an eDiary issued to patients from Visit 1 until Visit 4.

The LCQ is a quality of life measure of chronic cough. The questionnaire contains 19 items across 3 domains (physical, psychological, and social) to which the patient responds on a 7-point Likert response scale. The total score can range from 3 to 21 and domain scores can range from 1 to 7. Higher scores indicate a better quality of life. The LCQ will be completed at Visits 1, 2, 4, 5, and 6, and/or at the time of discontinuation of study drug.

The International Consultation on Incontinence Modular Questionnaire-Short Form (ICIQ-SF) is a questionnaire used to evaluate the frequency, severity, and impact of urinary incontinence on the quality of life. The questionnaire includes 3 items with responses measured on Likert scales, and one item that is measured via a qualitative response. The three nominal responses are summed to give the ICIQ score

(this total ICIQ-SF score can range from 0 to 21). The ICIQ-SF will be completed at Visit 2 and Visit 6, and/or at the time of discontinuation of study drug.

The Short-Form 36 (SF-36) Questionnaire is a widely used patient reported measure of overall health. The questionnaire consists of 8 scaled scores (health concepts) and evaluates vitality, physical functioning, bodily pain, general health perceptions, physical role functioning, emotional role functioning, social role functioning, and mental health. Scores for each scale range from 0 to 100; the lower the score, the greater the disability. The SF-36 measurements can be further characterized by 2 summary scores: the Physical Component Summary (PCS) and the Mental Component Summary (MCS). The SF-36 will be completed at Visit 2 and Visit 6, and/or at the time of discontinuation of study drug.

The Patient Global Impression of Change is a single-item questionnaire based on the Clinical Global Impression – Improvement scale, and it collects the patient's impression of overall improvement at Visit 6 and/or, if applicable, at the time of discontinuation of study drug. Responses are given on a 7-point Likert Scale, with lower scores indicating increasing degrees of improvement (1-3), 4 indicating no change, and higher scores indicating increasing degrees of worsening (5-7).

3.3. Treatments

S-600918 is formulated as a 50-mg orange, film-coated tablet. The placebo used in this study matches the S-600918 50-mg tablet in appearance. Patients will receive study treatment with S-600918 50 mg, S-600918 150 mg, S-600918 300 mg, or matching placebo, as follows:

- S-600918 50-mg group: 1 x 50-mg tablet and 5 placebo tablets once daily
- S-600918 150-mg group: 3 x 50-mg tablets and 3 placebo tablets once daily
- S-600918 300-mg group: 6 x 50-mg tablets once daily
- Placebo group: 6 x placebo tablets once daily

Treatment will be dispensed to patients at Visit 3 (Day 1), Visit 4 (Day 8), and Visit 5 (Day 22). Treatments will be packaged in identical blister cards within a wallet that will each contain 7 days of treatment plus 3 days of extra study drug in the event the patient cannot return for the next visit as scheduled. One wallet will be dispensed at Visit 3 and at Visit 5, and two wallets will be dispensed at Visit 4.

3.4. Dose Adjustment/Modifications

No dose adjustments or modifications are allowed in this study.

4. General Statistical Considerations

Unless otherwise noted, continuous variables will be summarized based on the number of non-missing observations (N), arithmetic mean (Mean), standard deviation (SD), median, minimum, and maximum values. Categorical variables will be summarized based on the frequency count and the percentage of patients in each category. All statistical tests will be performed at the 0.05 significance level using 2-sided tests, unless otherwise noted, and statistical testing will not be adjusted for multiple comparisons.

Study data will be presented in by-patient data listings. In general, all tables will be presented by treatment group. Individual patient data, PK data, and any derived data will be presented by treatment group (study drug) (S-600918 50 mg, S-600918 150 mg, S-600918 300 mg, and placebo). All analyses and tabulations will be performed by using SAS Version 9.2 or higher and WinNonlin Version 6.3 or higher.

Baseline will be defined as the last valid assessment recorded prior to the first administration of study drug unless otherwise specified.

For summaries, patients will be counted only once within each planned visit. In these summaries, the visit windows will follow the windows given in the protocol, which are repeated in Appendix 1 of this SAP. However, +1 day will be allowed at the end of the Visit 6 time window for analysis.

Visit	Target Day	Window Start Day	Window End Day
Visit 1 / Screening	-18	-28	-18
Visit 2 / Day -1	-1	-1	-1
Visit 3 / Day 1	1	1	1
Visit 4 / Day 8	8	6	10
Visit 5 / Week 3	22	20	24
Visit 6 / Week 4	27	25	28

Table 4-1: General Analysis Visit Wind

In the event that more than one observation is recorded within one of these windows, then, among these records within the window, the record occurring at the planned visit in the CRF will be used. If no records occurred at the planned visit within the window, then records occurring at any unplanned visits within the visit window will be considered, and the record occurring closest in time to the target visit day will be used. Results that are recorded at an Early Discontinuation visit may be summarized at a planned visit if the Early Discontinuation visit falls within the window for the planned visit, and the planned visit has not occurred.

Study days will be calculated using the date of the first administration of study drug as follows:

- If the assessment occurs on or after the date of the first administration of study drug, study day = (date of assessment – date of first administration of study drug) + 1
- If the assessment occurs prior to the date of the first administration of study drug, study day = date of assessment – date of first administration of study drug

Summaries presented by visit will only present the visits for which the parameter was planned to be collected. Listings of data collected at study visits will include all such data, regardless of whether it was planned to be collected during that visit.

Certain regional guidelines provide that patient reported outcomes (PROs) can be re-entered, or corrected, by the patient after the initial entry. This study uses several PROs, such as VAS, LCQ, ICIQ-SF, SF-36, PGIC, and Taste Questionnaire. As such when the original data are corrected, analyses will be conducted that use the latest available corrected data. For patients who did not correct their original entry, their original entry will be used in these analyses of corrected data. Additional analyses of only the original data will also be performed.

The following conventions define how the original data and corrected data will be analyzed. If there are no data corrections, then these conventions do not apply.

Analyses on the full analysis Set will use the latest corrected data, regardless of when the correction was obtained. A footnote to all tables containing corrected data will note how many instances of corrected data were included. These analyses will be included in the body of the CSR and will be the basis of hypothesis testing.

These analyses will be repeated using the original entries. Any differences in inference between the analysis of the corrected data and analysis of the original data will be noted in the CSR.

There is no plan for analyzing the PRO data using a Per Protocol Set. However, if this plan changes during or after the study, the Per Protocol Set will use corrected data only if the corrected data falls within the protocol defined window for a visit. Corrected data collected outside a visit window will not be

included in the Per Protocol Set population. A supplemental Per Protocol Set analysis will be conducted using only the original collected data. Any difference in the conclusions based on the Per Protocol Set between the use of the original and corrected data will be noted in the CSR if the CSR has not yet been completed.

In principle, missing data will not be imputed.

4.1. Sample Size

The sample size has been determined using the results of the VA322 proof-of-concept study. In that VA322 study, the mean (\pm SD) of the common log-transformed ratio of cough frequencies per hour in 24 hours after 2 weeks of treatment to that at baseline was -0.327 (0.379) in the S-600918 150-mg treatment (N = 31) and -0.160 (0.363) in the placebo treatment (N = 30). The difference in the common log-transformed ratio of the cough frequencies per hour in 24 hours after 4 weeks of treatment to that at baseline between each S-600918 dose group and placebo and the standard deviation (SD) in each treatment group in the Phase 2b study were assumed to be the same as those after 2 weeks of treatment observed in the proof-of-concept study, and -0.163 and 0.371, respectively. As a result, the effect size, ie, the difference divided by the SD, was determined to be -0.44. Based on this assumption, the sample size required to assure 80% power with a 2-sided 5% level of significance was calculated to be 83 patients per treatment group. Allowing for exclusion of 10% of patients per treatment group, 93 patients per treatment group will be needed. Therefore, the planned sample size at randomization was determined to be a total of 372 patients.

4.2. Randomization, Stratification, and Blinding

Patients who meet screening criteria at Visit 3 will be randomized in a 1:1:1:1 allocation to the 4 treatment groups (described in detail in section 3.3). The randomization will be stratified based on region (Japan, Europe, or the United States) and hourly cough count based on the 24-hour cough count recording at Visit 1 (≥30 coughs/hour or <30 coughs/hour) and will be performed by Interactive Response Technology (IRT).

The study will be conducted in a double-blind manner. Placebo tablets will match in appearance the S-600918 50-mg tablet, and the labeling and packaging of S-600918 and placebo will be identical. Section 3.3 of this SAP describes how treatment is packaged to achieve the dose-levels of S-600918 used in this study.

The randomization schedule will be maintained by IRT until data lock, as specified in the IRT User Manual. Except for unblinded sponsor staff (e.g., the Investigational Medicinal Product Manager) or designees, the sponsor and the sponsor's designees, the investigator, and all study-site personnel will be blinded to treatment assignment until data lock. As plasma drug concentration data may reveal the study treatment to which a patient was randomized, only the sponsor's bioanalytical expert will be provided these data prior to data lock to determine whether the bioanalysis is conducted appropriately. After data lock of all eCRF data, the sponsor will obtain the randomization schedule and all data from the IRT.

Unblinding at the request of an investigator should occur only in the event of an emergency, pregnancy of a patient, or an adverse event for which it is necessary to know the study drug to determine an appropriate course of therapy. Prior to unblinding and if the situation allows it, the investigator should contact the Medical Monitor. If the investigator judges it necessary to know the randomization code for a specific patient, the investigator will obtain the randomization code through the IRT, which will capture (at a minimum) the date and time of unblinding and the reason for unblinding. If the investigator is unable to speak with the Medical Monitor prior to unblinding, the investigator must notify the site monitor or the Medical Monitor as soon as possible after unblinding, WITHOUT revealing the treatment assignment for that patient. Procedures for emergency unblinding are specified in the IRT User Manual. The patient

should remain in the study and complete all study events and activities after unblinding, even if treatment is discontinued.

Patients who are unblinded at the request of an investigator will be summarized and listed and described in the Clinical Study Report (CSR).

4.3. Analysis Sets

The analysis sets define the groups of patients that will be analyzed and presented in the tables, listings, and figures that are described in this SAP. Patients will be listed along with their inclusion or exclusion in each of the analysis sets defined in this section.

4.3.1. All Randomized Population

The all randomized population will include all patients who are randomized to a treatment. Presentations based on this set of patients will group patients according to their randomized treatment.

4.3.2. Full Analysis Set (FAS)

The FAS will include all randomized patients who receive at least 1 dose of study drug and who have accepted cough monitor assessment at both baseline and at least 1 visit after initiation of study drug. Presentations based on this set of patients will group them according to their randomized treatment. The primary efficacy analysis will be performed on the full analysis set as well as the per protocol set (below). The primary hypothesis will be tested using the FAS. Patients in the all randomized population who fail to meet these criteria for entry in to the FAS will be listed with their reason(s) for exclusion from the FAS.

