7.4.1 Number of Coughs (VitaloJAK™ Cough Monitor)

The number of coughs over a 24-hour period will be recorded at Visit 1, Visit 2, Visit 4, Visit 5, and Visit 6 with the VitaloJAKTM cough monitor [27]. This cough monitor has CE marking in the European Union and 510(k) approval from the United States Food and Drug Administration (FDA).

The cough monitor will be applied to the patient at each of these visits, and the patient will be instructed to remove the monitor after 24 hours. Instructions for the application of the cough monitor to the patient are specified in a separate document.

If, based on initial assessment at the study site, the cough count recording at Visit 1 or Visit 2 is considered to have failed for any reason, the recording may be repeated (see details for Visit 1 in Section 8.1 and for Visit 2 in Section 8.3). Repeat recording of the cough count is not permitted at any other visits in the study.

Data collected with the cough monitor will be sent from the study site to the cough monitor analysis institution via the web portal of that institution. The number of coughs will be measured (including classification of awake and asleep hours) by cough analysis technicians for each of the following periods:

- 24 hours
- Waking hours
- Sleeping hours

The number of coughs will be reported by the cough monitor analysis institution to the sponsor, with counts provided for each 24-hour period and for the waking hours and the sleeping hours within each 24-hour period. Procedures regarding the cough monitor analysis are specified in a separate document.

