7.4.2.2 Daily Severity of Cough (eDiary)

The patient will be instructed to record daily the severity of cough on the preceding day (ie, prior 24 hours) on the VAS in the eDiary, starting at Visit 1 and continuing up to Visit 4 (ie, through Day 7) and/or, if applicable, at the time of discontinuation of study drug.

Data collected with the eDiary will be automatically uploaded from the device to the database maintained by the device vendor. Procedures regarding the eDiary are specified in a separate document.

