For all efficacy analyses, baseline is defined the last assessment before first dose of study drug, unless otherwise noted. All efficacy analyses will be presented for FAS, and, where noted, for the PPS. When the framework described for the primary analysis (which is also used in several subsequent analyses) is applied to cough count data, if any patient has an average coughs per hour at any baseline or post-baseline measurement that is zero, a correction factor of 0.1 will be added to all observed average coughs per hour values for all patients. A correction factor of 0.1 is necessary because these counts are log-transformed for the purposes of analysis, and log₁₀(0) is undefined. This handling is applied in the same manner to average coughs per hour in 24 hours, while asleep, and while awake. In principle, efficacy analyses will be based on data compliant with the analysis visit window at each visit in the treatment period for both of FAS and PPS (see section 4 of this SAP). For this reason, data outside the analysis visit windows will be regarded as missing.

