8.2.3. Analysis of Cough Severity (VAS)

The change in weekly cough severity at Visit 4, Visit 5, and Visit 6 to that at baseline will be analyzed using the primary analysis framework for the FAS. Similarly, the change in daily cough severity from Day 1 through Day 7 will be analyzed using the primary analysis framework for the FAS, only using Day 7 in place of Visit 6.

Both weekly and daily cough severity will also be summarized using descriptive statistics at each planned assessment by treatment group for the FAS.

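### Early patient-reported scores (daily VAS, and some weekly VAS and LCQ) are left out of analysis when a patient has no accepted cough recording after dosing

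*SAP*

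**What the plan says.** **Population.** SAP 4.3.2 admits to the FAS randomised patients who took at least one dose and "who have accepted cough monitor assessment at both baseline and at least 1 visit after initiation of study drug". Protocol 9.3 has the same structure. The opening of SAP section 8 states that "All efficacy analyses will be presented for FAS, and, where noted, for the PPS". SAP section 4 bases hypothesis testing of the patient-reported outcomes on the FAS and plans no per-protocol analysis of them. SAP 8.2.3 and 8.2.4 name the FAS again for the VAS and LCQ. The daily VAS change over the first week "will be analyzed using the primary analysis framework for the FAS, only using Day 7 in place of Visit 6".

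**Collection of the scores.** Protocol 7.4.2.2 sets the period for the daily VAS entries: "starting at Visit 1 and continuing up to Visit 4 (ie, through Day 7) and/or, if applicable, at the time of discontinuation of study drug". Weekly VAS and LCQ are completed at Visits 4, 5 and 6 and at the Early Discontinuation Visit. ICIQ-SF, SF-36 and PGIC have post-dose values only at Visit 6 or at discontinuation.

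**Collection of the recordings.** Post-dose recordings take place at Visits 4, 5 and 6 (target Days 8, 22 and 27; SAP 3.2.1). For a failed post-dose recording, Protocol 7.4.1 says: "Repeat recording of the cough count is not permitted at any other visits in the study." SAP Appendix 2 treats a rejected count as missing. After stopping drug, a patient is directed to the Early Discontinuation Visit and Visit 7 (Protocol 4.5.2). Protocol 8.7, 8.8 and Appendix 1 provide for collecting a monitor at those visits, not for applying one.

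**The concern.** The FAS definition suits a cough-count endpoint, but here it also decides who counts for different instruments. Whether a patient later yields an accepted recording is a post-randomisation event. For the daily VAS it normally comes after the endpoint has been observed. Removing observed scores on that basis weakens the randomised comparison, and the patients most exposed are those who stop in the first week.

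The study selects a dose, comparison with placebo on cough severity and LCQ is a secondary objective, and the daily VAS is its measure of early symptom change. Unequal early stopping across the four groups could affect that comparison, and no planned analysis would show it.

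**Working it through.** **1. The plan's own figure.** Inputs (Protocol 9.2, SAP 4.1): difference 0.163, SD 0.371, two-sided 5%, power 80%, exclusion 10%.
- Effect size: 0.163 / 0.371 = 0.44.
- Two-sample t-test: 82.05 per group, rounded up to 83.
- Inflation: 83 / 0.90 = 92.2, rounded up to 93; 4 × 93 = 372.

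The stated 83, 93 and 372 reproduce. The allowance is 93 − 83 = 10 patients per group.

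**2. Order of events.** The last diary day is Day 7. The first qualifying recording starts at Visit 4, target Day 8, window Day 6 to Day 10 (SAP Table 4-1). If Visit 4 falls on Day 6 or 7, the recording can overlap the last diary days. Otherwise the diary endpoint is complete first.

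**3. Early Discontinuation scores.** The visit is due on the day of the last dose, with a window of +3 days (Protocol Table 7-2, Appendix 1). With the last dose on Day d, it falls on Day d to Day d + 3. SAP section 4 lets its results count at a planned visit if they fall in that visit's window and the planned visit did not occur.
- Visit 4 window: d + 3 ≥ 6 requires d ≥ 3. With d = 5, the visit falls on Days 5 to 8, and a weekly VAS or LCQ from Day 6, 7 or 8 could serve as a Visit 4 value.
- Visit 6 window (Days 25 to 28): d + 3 ≥ 25 requires d ≥ 22. A patient who stops before an in-window Visit 4 has d ≤ 9, so the visit is on Day 12 at the latest. SAP section 8 treats out-of-window values as missing, so this patient has no usable ICIQ-SF, SF-36 or PGIC under any population.

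**4. Who is kept and who is lost.**

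| Patient | In FAS? | Observed, usable scores left out |
|---|---|---|
| Visit 4 recording fails, Visit 5 or 6 accepted | Yes | None |
| Stops drug on the day of Visit 4, at the site | Yes, if the Visit 4 recording is accepted | None in that case |
| Stops between visits before Visit 4 | No | Daily VAS; weekly VAS and LCQ if in the Visit 4 window |
| Attends visits, no accepted post-dose recording | No | Daily VAS, weekly VAS, LCQ; ICIQ-SF, SF-36 and PGIC if Visit 6 values exist |

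**5. Planned analyses that might restore them.** The two carried-forward sensitivity analyses (SAP 8.1.2) cover the primary endpoint within the FAS, and the per-protocol set is a subset of the FAS (SAP 4.3.3). Neither restores these scores.

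**6. Outer bound on precision.** Standard error is proportional to 1/√n. If the whole allowance were lost to the FAS and all of it recoverable for a patient-reported endpoint, the ratio would be √(93/83) = 1.059, about 6%. At an assumed effect size of 0.44 (taken from cough counts, not the VAS), t-test power would be 80.5% with 83 per group and 84.7% with 93.

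**The case against.** The strongest reply is that the effect is small and mostly confined to one secondary endpoint. Any one accepted recording at three visits suffices, and acceptance is easy on length: SAP Appendix 2 sets no minimum for the rate calculation and mentions rejection only below 1 hour of data. An early stopper has no on-treatment Day 7 diary score, so would affect the Day 7 contrast only through the mixed model's covariance. For weekly VAS and LCQ, such a patient adds a Visit 4 value at most. Exclusions from the FAS are listed with reasons, and by-patient listings are planned. Protocol 9.10 makes the FAS the primary efficacy population, so a change is a departure from the protocol. All of this stands, and it limits the size of the point. It does not explain why observed scores should depend on another instrument, and listings are not an analysis.

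Three stronger readings are tempting but unsupported:
- **That the Day 8 recording alone decides.** It does not; Visits 5 and 6 also qualify.
- **That all five instruments suffer alike from early stopping.** Step 3 shows that three of them do not.
- **That active doses are flattered by a known amount.** Assuming exclusions of 3% to 8% on active and 1% on placebo, and excluded patients 10 to 20 mm worse, gives (0.03 − 0.01) × 10 = 0.2 mm to (0.08 − 0.01) × 20 = 1.4 mm. None of these inputs is in the documents. The formula describes a simple mean of observed scores, not the Day 7 mixed-model contrast. Stopping for intolerance need not mean worse cough, so the sign could reverse.

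The need for a baseline cough count does not justify the post-dose condition. Inclusion criterion 6 requires a Visit 1 count, and SAP 8.1 falls back to it. Nor is imputation needed, since the repeated-measures model can use partial diary data.

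**Conclusion.** The point holds as a matter of structure. Observed scores for the daily VAS, and some for the weekly VAS and LCQ, are left out according to a post-randomisation event on a different instrument, and no planned analysis brings them back. ICIQ-SF, SF-36 and PGIC are touched only where a patient has usable scores but no accepted post-dose recording.

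The size is unknown. The documents give no first-week stopping rate and no rate of rejected recordings. The 6% in standard error is an outer bound: the 10% allowance is general, is not attributed to the monitor, and would include dropouts who lack later patient-reported values anyway. Bias in a treatment comparison arises only if the share excluded, or the gap between excluded and retained patients, differs between arms. The documents settle neither its direction nor its amount. The primary endpoint is not affected by this point.

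**What to change.** In SAP 8.2.3 and 8.2.4, analyse daily VAS, weekly VAS and LCQ by randomised group in all randomised, dosed patients with a baseline and at least one post-dose in-window value of that instrument. For the daily VAS, that value is a post-dose diary entry through Day 7. Keep the same mixed model, without imputation, and use the available pre-dose cough count where a covariate or stratum needs one. Present the cough-monitor FAS result alongside. Record the departure from Protocol 9.10 in SAP section 13, which at present reports no changes.

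ICIQ-SF, SF-36 and PGIC can stay on the FAS. The planned listing of FAS exclusions will identify patients without an accepted post-dose recording, who can then be checked for Visit 6 scores.

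The cost is SAP wording, one population flag and the section 13 entry, with no new data. The downside is slightly different denominators between the patient-reported and cough-count tables.
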